#### Pooled analysis

See Annex 2 for data management of pooled data and Annex 3 for pooled data analysis.

#### Pandemic vaccine

For the pooled data, interim analyses will be conducted in different periods according to the available sample size. Based on the available sample size, different outputs will be estimated in each of the interim analyses. For each output, a minimum of 90 cases and 90 controls will be needed (assuming a vaccination coverage in the source population of 50% and a detectable OR of 0.4; see Table 1 on 'sample size calculations').

#### Table 2: Sample size calculation

Proportion vaccinated	OR	Number of cases	Number of controls
0.5	0.4	89	89

#### Table 3: Sample size interim analysis

Outputs	Sample size needed in pooled data	Sample size needed for each individual site
Pooled crude VE for all vaccines and target groups	90 cases*	
Pooled adjusted VE for all vaccines and target groups	90 cases*	
Pooled VE stratified by specific variables (e.g. age group, target group)	90 cases per stratum*	
Crude VE by study site for all vaccines and target groups		90 cases per study site
Pooled adjusted VE for all vaccines and target groups		90 cases per study site
Stratum-specific, site-specific VE (e.g. age group, target group		90 cases per study site and stratum
Pooled brand VE	90 cases for each specific brand analysis*	
Pooled brand analysis stratified by specific variables	90 cases per stratum for each specific brand analysis*	
Site-specific, brand-specific, stratum- specific VE (e.g. age group, target group)		90 cases per study site and stratum for each specific brand analysis

\* Using one-staged pooled analysis (see Annex 3 for further details)

The timing to conduct each interim analysis will depend on the time needed to reach the appropriate sample size. This will depend mainly on the ILI incidence, the influenza incidence, the vaccination coverage, and the swabbing scheme used by GPs and the number of GPs (see Excel calculator, attached to the PDF version of this document).

The sample size suggested for brand-specific VE is an estimate and cannot be precisely defined at this stage. The sample size for brand VE will depend on the vaccination coverage for each brand and therefore on the market share.

## 3.14 Data management

#### Individual analysis

EpiConcept will provide the option of web-based data collection methods, if so desired by the countries. These methods can also be combined with paper-based methods.

If EpiConcept's web-based data collection methods will be not used, data can be coded as outlined in Annex 1. Alternatively, study teams can provide EpiConcept with a codebook that includes the variable names, variable descriptions, and the coding of variable values.

## **Data cleaning**

Summary and frequency tables as well as visual representations of appropriate variables will be used to find illegal, implausible or missing values within the dataset. Checks for inconsistencies will be carried out (e.g. date of swabbing before date of onset of symptoms). These values will be checked against the questionnaires or queried with the GP. Any changes to the data will be documented and stored separately from the crude database. Any recoding of data (e.g. age) is documented. A guide and/or an example Stata do-file for data cleaning will be provided if so desired.

#### **Pooled analysis**

EpiConcept conducts the pooled analysis. Each individual study will be sent to EpiConcept's study database. All personal identifier information such as names, addresses, and medical registration codes will be deleted before data transmission to EpiConcept, where all individual data will be pooled. A country (or study) identifier will be included in each record (e.g. ESP for Spain, UK for the United Kingdom), a GP code will be included (e.g. a unique number), and each record will be given a unique number. This number will also be included in the study team's database and will be used by EpiConcept and the study teams during pooling, so that records can be traced back whilst maintaining anonymity, if there should be any further queries. Study databases can be sent to EpiConcept in any format. EpiConcept will perform all necessary data cleaning. EpiConcept will document and share any further data cleaning and analysis with all study coordinators to ensure it can be reproduced.

See Annex 3 for detailed guidelines on the pooled analysis.

#### **Missing data**

Any missing data will be documented.

If many data are missing and/or there is evidence of bias in the missing data, and variables that are considered good predictors of the missing data are available, multiple imputation methods at study level will be used to replace missing values.

A sensitivity analysis will be carried out comparing results from the complete case analysis (where records with missing data will be dropped) and the full set analysis (with imputed data).

## 3.15 Potential biases

## Negative confounding

Negative confounding refers to biases that reflect the fact that high risk groups will be more likely to be vaccinated and therefore reduce VE.

## Positive confounding

Positive confounding refers to biases that reflect a 'healthy vaccine effect'. People with a healthy lifestyle will be more likely to accept/request vaccination, thus leading to an increase of measured VE.

Positive and negative confounding will be minimised through stratification and multivariable analysis (including presence of chronic diseases) as well as variables that will be collected in order to measure positive and negative

confounding. It will not be possible to rule out the presence of characteristics in the study population for which no information is collected in the study questionnaire and that therefore could lead to positive or negative confounding. Therefore, residual positive or negative confounding may be present. A sensitivity analysis will be conducted to assess the effect of a potential and unmeasured confounding factor.

#### **Representativeness of cases**

The study includes only cases consulting a GP for ILI. In the context of the pandemic, health-seeking behaviour may differ by country depending on the case management strategy (e.g. recommendation of not seeing a GP). In some countries, only severe cases will consult a GP. In other countries, severe cases will directly report to emergency rooms without consulting their GPs. The type of cases included in the study should be described for each study and it should be noted how its representativeness may affect the VE estimates.

#### Pooled estimate and its bias

Any bias in the individual studies influences the pooled estimate. The power of the test for the presence of heterogeneity between individual studies will be low if there are few studies. In this case, the test may not detect the presence of heterogeneity, even if present. It is important that heterogeneity will also be assessed using qualitative knowledge about differences between studies. Depending on the nature of the bias, the inclusion of biased studies in the pooled estimate could lead to over- or underestimation of the true vaccine effectiveness.

## 3.16 Consent

According to country-specific regulations, informed (oral or written) consent will be required from each study participant.

**D** Details will be available in the study annexes.

## 3.17 Dissemination of results

The enrolment of cases/controls will be regularly updated by each study coordinator on the 'I-MOVE in Europe' web page (http://sites.google.com/site/epiflu).

Seasonal vaccine: First VE estimates (intra-seasonal) will be disseminated early during the influenza season; final estimates will follow at the end of the season.

Pandemic vaccine: First estimates will be disseminated once the sample size allows for meaningful interpretation (see paragraph on pooled analysis and Excel calculator attached to the PDF version of this document).

## Publications, scientific communication

Each study coordinator will decide where the results of the individual studies will be published and which scientific conferences will be attended in order to present the results. An article presenting the results of the pooled analysis and estimates for the EU/EEA will be submitted to a peer-reviewed journal. The list of authors will include one representative for each of the studies. Co-workers and contributors will be acknowledged. The actual authorship for the pooled article will be discussed with the study teams at the beginning of the study.

## 3.18 Training

Participating GPs will be trained on the study protocol before the start of the study. They will receive the protocol, questionnaires and laboratory swabbing procedures.

# **4 Logistical aspects**

## 4.1 Study leader

In each country, a principal investigator will coordinate the study at the country level and act as focal point for the European study. EpiConcept will be in charge of the pooled analysis.

## 4.2 Human resources

In each country, a part-time investigator will be in charge of monitoring data collection at the GP office level. GPs collect information among cases and controls. GPs could be offered a payment or compensation for their participation in the study.

**b** The specific human resources needed in each country will be detailed in the study annexes. EpiConcept will ensure the overall coordination of the various studies.

## 4.3 Supervision

Site visits and joint workshops will be organised by EpiConcept/Member States consortium in order to carry out an appraisal of the ongoing studies in the various countries involved. The appraisal team will be composed of two persons from the various project partners.

## 4.4 Questionnaires

Standardised questionnaires will be developed for the study. The variables used at the European level will be collected in the same way for each of the studies (see Annex 1: List of variables, definition and coding).

## 4.5 Computer support

Data collection and entry will be conducted at the country level. EpiConcept will provide a structured data entry form. For countries willing to submit data electronically, EpiConcept will provide an online questionnaire.

# 4.6 Consent

Each study will comply with national ethics committee requirements. Informed consent will be required from all participants. The national ethics committees will specify whether oral or written consent will be required.

## 4.7 Further studies

Further potential studies could focus on:

- comparing results obtained from all six control groups (ILI flu negative cases; random or systematic sample of GP patients seen at GP office; random sample of people from the catchment area of GPselected cases);
- comparing results obtained from various swabbing deadlines, e.g. 2, 3, or 4 days after onset of ILI;
- comparing vaccine status and severity of influenza cases selected through systematic or GP ad hoc selection of ILI cases;
- comparing acceptability and feasibility of various sizes of questionnaires to assess negative confounding;
- identify variables to assess the presence of positive confounding;
- acceptability of the study among GPs;
- comparing GP accessibility for different groups within the local population;
- any other topic that study teams consider helpful in interpreting the study results.

**b** Further potential studies will be detailed in the study annexes.

# 5 Budget

Funding can be used for:

- payment of study supervisor;
- payment of GPs;
- training of GPs; and
- financial support for laboratory tests.

**b** Each study group will provide a detailed budget in the study annexes.

vacc_07	Numeric (categorical)	0 = No 1 = Yes 8 = Do not know	Previous seasonal influenza vaccination 2007-08
anemia_spleen	Numeric (categorical)	0 = No 1 = Yes 8 = Do not know	Enlarged spleen, anaemia
cirrhosis	Numeric (categorical)	0 = No 1 = Yes 8 = Do not know	Cirrhosis
diabetes	Numeric (categorical)	0 = No	Diabetes and endocrine
		1 = Yes 8 = Do not know	
heart_dis	Numeric (categorical)	0 = No 1 = Yes 8 = Do not know	Heart disease
hema_cancer	Numeric (categorical)	0 = No 1 = Yes 8 = Do not know	Hematologic cancer
immuno	Numeric (categorical)	0 = No 1 = Yes 8 = Do not know	Immunodeficiency and organ transplant
lungdis	Numeric (categorical)	0 = No 1 = Yes 8 = Do not know	Lung disease
nonhem_cancer	Numeric (categorical)	0 = No 1 = Yes 8 = Do not know	Nonhematologic cancer
pregn	Numeric (categorical)	0 = No 1 = Yes 8 = Do not know	Pregnancy
ren_disease	Numeric (categorical)	0 = No 1 = Yes 8 = Do not know	Renal disease
dem_stroke	Numeric (categorical)	0 = No 1 = Yes 8 = Do not know	Dementia, stroke
rheumat	Numeric (categorical)	0 = No 1 = Yes 8 = Do not know	Rheumatologic diseases
severity	Numeric (count)	integer	Number of hospitalisations previous year for the chronic disease
gpvisit	Numeric (count)	integer	Number of GP consultations previous year
fs_bath	Numeric (categorical)	0 = No 1 = Yes 8 = Do not know	Requires assistance to bathe

Variable name	Туре	Values and coding	Definition
fs_walk	Numeric (categorical)	0 = No 1 = Yes 8 = Do not know	Requires assistance to walk
smoking		0 = Never 1 = Former 2 = Current 9 = Do not know	Never, former (stopped smoking at least 1 year before inclusion in the study), current smoker
antivir	Numeric (categorical)	0 = No 1 = Yes 8 = Do not know	Administration of antivirals
antivirdate	Date	dd/mm/yyyy	Date administration antiviral
antivirtype	Text		Type of antiviral (brand name)
prev_h1n1	Numeric (categorical)	0 = No 1 = Yes 8 = Do not know	Lab-confirmed A(H1N1)v prior to study.
res_home	Numeric (categorical)	0 = No 1 = Yes 8 = Do not know	Exclusion criteria: living in a residential home
contra	Numeric (categorical)	0 = No 1 = Yes 8 = Do not know	Exclusion criteria: contraindication for influenza vaccination
dens_cc	Numeric (categorical)	0 = No 1 = Yes	Exclusion criteria for density case- control: ILI symptoms in the season

This table represents a selection of confounders. Variables can be included or excluded as necessary.

# Annex 2: Pooled data management

## Data preparation and transfer at study-level

Data validation, cleaning and verification will be carried out at study-level (for flow chart, see Annex 4). All personal identifier information such as names, addresses, medical registration codes will be deleted. A country (or study) identifier will be included in each record (e.g. ESP for Spain, UK for the United Kingdom), a GP code will be included (e.g. a unique number) and each record will be given a unique number. This number is also included in the study team database and will be used by EpiConcept and the study teams during pooling, so that records can be traced back whilst maintaining anonymity, if there are any further queries.

#### **Minimum dataset**

The minimum dataset will be transmitted to EpiConcept where individual data will be pooled, and includes:

- study identification: country and GP;
- case/control demographics;
- signs, symptoms;
- date of onset of ILI;
- date of swabbing;
- laboratory results;
- selected underlying conditions;
- number of hospitalisations for the chronic diseases in the previous year;
- number of GP visits in the previous 12 months;
- smoking history;
- current season influenza vaccination including date;
- pandemic vaccination including number of doses, date, brand;
- influenza vaccination in the previous two seasons;
- pregnancy status;
- functional status;
- antiviral administration; and
- information on laboratory-confirmed A(H1N1)v influenza since the beginning of the pandemic (or other date according to the duration of the pandemic).

For pandemic IVE estimates, data collected will be revised as more information on the vaccine and the target groups become available.

#### Data transfer

Study databases can be sent to EpiConcept in any format. The minimum dataset can be coded as described in Annex 1. Alternatively, a codebook can be provided to EpiConcept with the variable names, variable descriptions, and the coding of variable values.

## **Data cleaning**

EpiConcept will carry out data cleaning again, once the data are received. Summary and frequency tables and graphic displays of appropriate variables will be used to find illegal, implausible or missing values within the dataset. Checks for inconsistencies will be carried out (e.g. date of swabbing before date of onset of symptoms). Any improbable, illegal or missing values will be reported to the country in questions.

Any subsequent changes to the data will be fully documented and stored separately from the crude database, to ensure reproducibility and transparency of data management.

#### **Data recoding**

Variables will be recoded and new variables generated according to Annex 5. The recoded data will be stored separately from the crude data, and recoding will be documented.

#### **Missing data**

Great care will be taken to avoid missing data.

Baseline characteristics of records with missing data will be compared to records without missing data.

If many data are missing and/or there is evidence of bias in the missing data and variables that are considered good predictors of the missing data are available, then multiple imputation methods at study level will be used to replace missing values.

A sensitivity analysis will be carried out comparing results from complete case analysis (where records with missing data will be dropped) and full set analysis (with imputed data).

## Data appending and data flow

After data cleaning, the data will be appended, and a unique identifier for each GP will be created by concatenating the study code and the GP code. An example data flow chart is presented in Annex 4.

## **Annex 3: Pooled data analysis**

The main characteristics of each study will be summarized individually, including:

- number of GPs participating and catchment population;
- beginning of the pilot study;
- beginning of influenza period, peak, end;
- beginning of vaccination campaigns for seasonal and pandemic vaccine;
- target groups for the seasonal and pandemic vaccination;
- vaccine brands available;
- proportion of ILI flu positive among all ILI cases; and sample size.
- Analyses will be carried out first for each individual study and then, in a second step, a pooled analysis will be conducted.

Analysis will be done:

- on all data and separately with cases/control restricted to an interval between date of onset of symptoms and swab taken of <4 days;

- for overall VE and influenza type-specific VE if the sample size permits; and
- for the various types of pandemic vaccines, by age group targeted for vaccination.

All analyses will be carried out with Stata v10.1 (Stata Corp LP, College Station, TX, USA).

For methods on individual level analysis, see main section.

#### Testing for heterogeneity

Study-specific crude and adjusted ORs and their CIs will be plotted in separate forest plots. Following the core protocol will minimise heterogeneity between studies. However, adherence to the protocol will be checked, and study design and study quality characteristics will also be used to take a qualitative decision whether one or more studies are substantially different from the others and thus should be excluded from the pooled analysis.

Statistical heterogeneity between studies will be tested using Q-test and the  $I^2$  index (see boxes for formulae below). The Q-statistic follows a chi-squared distribution (with k–1 degrees of freedom). The Q-test reports presence or absence of heterogeneity, while the  $I^2$  index (based on the Q-statistic) quantifies the extent of the heterogeneity. According to the Higgens and Thompson classification, an  $I^2$  index of around 25% indicates low, 50% indicates medium and 75% indicated high heterogeneity between studies.

$$Q = \mathbf{a} w_i (\log(OR_i) - \log(OR_F))^2$$

Where:

$$w_i = 1/v_i$$

vi is the inverse variance of the estimated log odds ratio of study i.

$$\log(OR_F) = \frac{\mathbf{\mathring{a}} \ w_i \ \mathbf{i} \ \log(OR_i)}{\mathbf{\mathring{a}} \ w_i}$$

$$I^{2} = \frac{Q - (k - 1)}{Q} , 100\% \text{ for } Q > (k - 1)$$
$$I^{2} = 0 \text{ for } Q \pounds (k - 1)$$

Formulae are given here for completeness, in practice these measures are automatically calculated by many statistical software packages as part of the meta-analysis commands.

## Two-stage pooling approach

If adequate sample size by study is achieved to obtain an adjusted OR, then a two-stage approach to pooled analysis will be taken. Studies considered to be heterogeneous will not be included in the two-stage model.

Study-specific adjusted ORs and standard errors for the effect of current influenza vaccination obtained from the individual studies will be combined in a model that incorporates random effects of the studies, to account for unmeasured country- and study-specific factors that differ between studies.

The study-specific exposure-disease effects (ORs) will then be weighted by the inverse of their marginal variances. The marginal variance is the sum of the individual study-specific variances and the variance of the random study effects ( $\tau^2$ ). This will give the pooled odds ratio and standard error. See Annex 6 for an example of Stata syntax.

$$\log(OR_R) = \frac{\mathbf{\mathring{a}} \ w_i \ast \log(ORi)}{\mathbf{\mathring{a}} \ w_i \ast}$$
$$wi^* = \frac{1}{vi + t^2}$$

The study-specific ORs and their CIs, along with the pooled odds ratio, will be presented graphically in a forest plot. This model will also be compared against a two-stage analysis with fixed study effects, to assess the effects of model assumptions.

If despite the common protocol, covariates were not uniformly collected in the different studies, then an analysis will be carried out excluding certain studies, and a comparison to the analysis including all studies will be made. In a different scenario, analyses can also be carried out excluding certain study participants for whom variables were collected differently.

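### The two-stage pooled model leaves out studies considered heterogeneous without limiting the grounds, so exclusion may follow the study ORs and make the pooled VE interval too narrow

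*Protocol*

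**What the plan says.** Annex 3 of the Protocol deals with differences between studies in two consecutive subsections.

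- **Testing for heterogeneity.** Study-specific crude and adjusted ORs are shown in forest plots. Protocol adherence is checked, and design and quality are considered, with this aim: "take a qualitative decision whether one or more studies are substantially different from the others and thus should be excluded from the pooled analysis". A separate paragraph adds: "Statistical heterogeneity between studies will be tested using Q-test" and the I² index. For I² it gives only descriptive bands: an "index of around 25% indicates low, 50% indicates medium and 75% indicated high heterogeneity between studies". No value of Q or I² is linked to an action.
- **Two-stage pooling approach.** The rule here is unqualified: "Studies considered to be heterogeneous will not be included in the two-stage model". The study-specific adjusted ORs are then "combined in a model that incorporates random effects of the studies, to account for unmeasured country- and study-specific factors that differ between studies". On the weights: "The marginal variance is the sum of the individual study-specific variances and the variance of the random study effects".

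Section 3.15 (Pooled estimate and its bias) warns that the heterogeneity test has low power with few studies. It asks for qualitative knowledge to be used as well as the test.

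Two comparisons are planned. The random-effects model is compared with a fixed-effects version. A comparison with all studies is promised only where covariates were not collected uniformly.

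**The concern.** The random effects are there "to account for unmeasured country- and study-specific factors that differ between studies". If studies leave because their ORs differ from the rest, the spread that τ² should measure is removed before τ² is estimated. The interval then shrinks while the real uncertainty about the average effect does not. The pooled VE also comes to depend on which countries were dropped.

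The text leaves this open. The pooling subsection does not say that a study counts as heterogeneous only on the adherence, design and quality grounds given just before. Individual studies are analysed first (section 3.13), so their ORs are known when the judgement is made, and nothing requires it to be made without sight of them. The stratified analyses use the same two-stage method, so different strata could pool different sets of countries.

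Neither planned comparison would generally reveal the effect. Random versus fixed is run on the studies already retained, and the all-studies comparison covers a different problem.

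**Working it through.** **1. Precision of one study.** Section 3.13 asks for at least 90 cases and 90 controls, assuming 50% vaccine coverage and OR 0.4. Table 2 gives 89 and 89.

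- Vaccinated proportion in controls: 0.5. In cases: 0.4/(1 + 0.4) = 0.2857.
- The two-proportion formula (two-sided α 0.05, power 0.80) gives 81 per group without continuity correction. With it the result is 89.4, that is 89 or 90 depending on rounding. The plan's figure is reproduced.
- Variance of one study's log OR with 90 + 90: v = 1/25.7 + 1/64.3 + 1/45 + 1/45 = 0.0989.

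**2. Worked example (assumed ORs 0.30, 0.35, 0.40, 0.45 and 1.00, each 90 + 90).** The weights are the plan's 1/(v + τ²), with the DerSimonian-Laird τ².

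- *All five.* Mean log OR −0.794 and sum of squared deviations 0.879, so Q = 0.879/0.0989 = 8.89 on 4 df (p = 0.064) and I² = (8.89 − 4)/8.89 = 55%. With equal variances τ² = 0.879/4 − 0.0989 = 0.121. SE = √((0.0989 + 0.121)/5) = 0.210. Pooled OR 0.452, VE 54.8% (95% CI 31.8 to 70.0).
- *Fifth study dropped.* Mean log OR −0.992, Q about 0.9 on 3 df, so τ² = 0 and I² = 0. SE = √(0.0989/4) = 0.157. Pooled OR 0.371, VE 62.9% (49.5 to 72.8).

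One exclusion raises the pooled VE by 8 points, shortens the interval from 38.2 to 23.3 points and makes the evidence of heterogeneity disappear. A cut-off of p<0.10 would flag this set; p<0.05 would not.

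**3. Long-run coverage (simulation, 6,000 runs per setting in the main run).** From the Protocol: 90 + 90 per study, 50% coverage, mean OR 0.4, weights 1/(v + τ²). Assumed, because the Protocol does not give them: k = 5 studies (the number of 2008-09 pilots in section 1), τ on the log-OR scale, and dropping the largest Q contributor while Q p<0.10.

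| τ | Typical I² = τ²/(τ² + 0.0989) | Coverage, all kept | Coverage after dropping |
|---|---|---|---|
| 0 | 0% | 96% | 95% |
| 0.2 | 29% | 94% | 90% |
| 0.3 | 48% | 92% | 82% |
| 0.4 | 62% | 91% | 75% |
| 0.6 | 78% | 89% | 58% |

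At τ = 0.4 (true τ² 0.16) the mechanism is visible:

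- At least one study is dropped in 54% of runs.
- Mean estimated τ² falls from 0.154 to 0.028.
- Mean interval width on the log scale falls from 0.847 to 0.681.
- The actual SD of the pooled log OR rises from 0.224 to 0.303.

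**4. Sensitivity to the assumed rule (τ = 0.4, k = 5).** Coverage is 78% with Q p<0.05, 74% with I²>50% and 68% with I²>25%. With k = 8 the range over all the rules tried is 67% to 78%, against 91.5% with all studies kept.

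**The case against.** The strongest reply is that the plan can be read coherently. The only grounds explicitly tied to exclusion are adherence, design and quality. Q and I² follow in a separate paragraph that attaches no exclusion to them, and the Q-test speaks to the set of studies, not to any one of them. On that reading known differences lead to exclusion and random effects absorb the unmeasured remainder. Exclusion on those grounds alone, decided without sight of the ORs, would not produce the narrowing shown above. Section 3.15 also gives a fair reason for being able to exclude: a biased study can distort the pooled VE.

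This stands as a possible reading, and it rules out saying that the plan prescribes dropping outlying ORs. It does not remove the point. The sentence in the pooling subsection is unqualified, section 3.15 and the preceding subsection let heterogeneity be judged statistically as well, and no timing or criteria confine the decision. It is an affirmative rule, not a detail left open for a later document.

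A reader might also infer that a country with low VE would go unreported. The documents do not support this: country VE is a secondary objective (section 2.2), each study is analysed on its own (section 3.13), and study-specific ORs are plotted (Annex 3). Nor do they fix the number of studies for 2009-10. Five is the pilot count, and the four country names in Annex 6 are placeholders.

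**Conclusion.** The point holds as a defect in an unqualified rule that permits exclusion on results. If exclusion follows the ORs, the pooled VE depends on which countries are dropped and its nominal 95% interval is too narrow. Under the stated assumptions coverage is about 82% against 92% at τ = 0.3, and about 75% against 91% at τ = 0.4. With no true heterogeneity the harm is small (95% against 96%). These figures illustrate what the wording allows; they do not forecast what the study teams will do.

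The scope is limited to the two-stage model. The one-stage fallback for small samples, and the pooled interim outputs in Table 3 marked as one-stage, do not use this sentence.

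A reader might take the shortfall with all studies kept (89% to 91% at τ = 0.4 to 0.6) as part of the same fault. It is a separate question about how the interval is computed. The pooling subsection names no interval method, and the Annex 6 syntax is offered only as guidance.

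**What to change.** Replace the sentence in Two-stage pooling approach and align the exclusion clause in Testing for heterogeneity so that:

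1. the primary two-stage random-effects model includes every eligible study;
2. a study may be excluded only for design, quality or adherence failures listed in advance, with the decision recorded without sight of that study's OR;
3. any other exclusion, for example leave-one-out, is a sensitivity analysis shown beside the all-studies estimate;
4. τ² is reported with the pooled VE, and Q and I² remain descriptive.

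Both subsections need the change, because removing the one sentence would leave the exclusion clause in the other unclear on timing and grounds. The cost is a few sentences and an agreed list of disqualifying failures. The pooled interval may be wider, and a study whose fault was not foreseen stays in the primary estimate; leave-one-out results would show its influence.
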